224 The same system is also currently the subject of a similar trial down to 6 years old (IDE#20 above).

225 Finally, preliminary analysis of a clinical trial in France using the same system in prepubertal
 226 children (6-10 yo) comparing 24/7 vs overnight use has shown very promising performances as
 227 well (Table 1).

228

Table 1: Interim analysis of FREELIFEKIDS AP (N=30 for 3 months)

	Overall					
	CLC at night		CLC 24/7		Stats	
	baseline	CLC	baseline	CLC	base vs Tx	Night vs 24/7
% time below 50mg/dL	0.4 ± 0.3%	0.3 ± 0.2%	0.5 ± 0.7%	0.3 ± 0.2%	ns	ns
% time below 54mg/dL	0.7 ± 0.6%	0.6 ± 0.3%	0.9 ± 1%	0.5 ± 0.4%	0.081	ns

CLINICAL PROTOCOL

% time below 60mg/dL	1.5 ± 1%	1.1 ± 0.5%	1.7 ± 1.6%	1.1 ± 0.8%	0.041	ns
% time below 70 mg/dL	4.1 ± 1.9%	2.8 ± 1%	3.9 ± 2.8%	2.8 ± 1.9%	0.006	ns
% time between 70-140mg/dL	42 ± 8.6%	45.6 ± 7.4%	37.9 ± 8.2%	49.3 ± 4.9%	<0.001	0.009
% time between 70-180mg/dL	63.2 ± 9.1%	67.5 ± 6.5%	59.7 ± 8.4%	71.8 ± 4%	<0.001	0.009
% time above 180mg/dL	32.8 ± 9.2%	29.6 ± 6.7%	36.4 ± 9.5%	25.4 ± 4.8%	<0.001	0.010
% time above 250mg/dL	9.6 ± 4.3%	8.6 ± 3.7%	11.8 ± 5.6%	6.1 ± 2.2%	0.001	0.010
% time above 300mg/dL	2.8 ± 1.7%	2.7 ± 1.8%	3.9 ± 3.7%	1.7 ± 1%	0.030	0.046
Average CGM [mg/dL]	158.1 ± 13.6	156.7 ± 10.5	165.4 ± 15.8	150.2 ± 7.4	0.001	0.006

229 We propose to use the Control-IQ System during a supervised 48 hours hotel stay with planned
 230 activities and meals; in addition, child participants will continue to use the system for another 3
 231 days at home under the parent/guardian(s) supervision.

232 **1.3 Primary Specific Aim**

233 Study the safety profile of the Tandem t:slim X2 with Control-IQ System in children with type 1
 234 diabetes aged 2-6 years old.

235 **1.4 Secondary Specific Aims**

- 236 • Assess the safety profile of the system at home under parental/legal guardian(s)
 237 supervision
- 238 • Compare system performance to normative data from a 6-12 years old cohort

239 **1.5 Study Design**

240 **1.5.1 Purpose/Objectives of Clinical Study**

241 The purpose of this study is to demonstrate the safety and efficacy the Artificial Pancreas system
242 (Tandem t:slim X2 with Control IQ Technology) in T1D participants, aged 2-6 y.o.

243 **1.5.2 Study Participants**

244 Approximately 15 participants with Type 1 Diabetes Mellitus, currently managed with insulin
245 pump therapy, will participate in the trial for approximately 14 days. The study will be performed

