246 at the University of Virginia, Stanford University, and the Barbara Davis Center at the University
247 of Colorado. Children and a parent/guardian(s) will use the system at home in Open Loop until the
248 start of the Hotel Admission. The child participant will then use the Control-IQ System during a
249 ~48 hours study hotel/house admission. The child participant will then use the Control-IQ System
250 at home for 72 hours under parental supervision and remote monitoring by the study team.

251 **1.5.3 Clinical Sites**

252 Each clinical site will perform the trial independently, seeking their own local IRB approval.

253 • The University of Virginia-Center for Diabetes Technology

254 • [name]

255

256 • Stanford University

257 • [name]

258

259 • Barbara Davis Center for Diabetes, University of Colorado Anschutz Medical Campus:

260 • [name]

261 **1.5.4 Study Diagram**

[figure not shown]

Figure 2: Study Diagram

265 **Chapter 2: STUDY ENROLLMENT AND SCREENING**

266 **2.1 Participant Recruitment and Enrollment**

267 Enrollment will proceed with the goal of completing 15 participants in this trial, approximately 5
268 participants per clinical site.

269 Enrollment at the University of Virginia will be defined as a parent/child dyad as the parent is
270 completing the questionnaire at the conclusion of the study.

271 Up to 25 participants may sign the consent form.

272 **2.2 Informed Consent and Authorization Procedures**

273 Consenting procedures and documentation is defined in section 15.3.

274 **2.3 Participant Inclusion Criteria**

275 Child participants must meet all of the following inclusion criteria in order to be eligible to
276 participate in the study.

- 277 1. Age \geq 2 and $<$ 6 years old at the time of consent
- 278 2. Clinical diagnosis, based on investigator assessment, of type 1 diabetes for at least 3 months
279 and using insulin at the time of enrollment
- 280 3. Use of an insulin pump in the past 3 months
- 281 4. Use of Dexcom G6 for at least 11 out of the last 14 days
- 282 5. Parent/guardian(s) have familiarity with and use of carbohydrate ratios for meal boluses
- 283 6. Living with one or more parent/guardian knowledgeable about emergency procedures for
284 severe hypoglycemia and able to contact emergency services and study staff

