1068 Participation in the study is voluntary, and a participant may withdraw at any time. For participants
1069 who withdraw, their data will be used up until the time of withdrawal.

1070 **12.3 Confidentiality**

1071 For security and confidentiality purposes, subjects will be assigned an identifier that will be used
1072 instead of their name. Protected health information gathered for this study may be shared with the
1073 third party collaborators. De-identified subject information may also be provided to collaborators
1074 involved in the study after the appropriate research agreement has been executed.

1075 **Chapter 13: STATISTICAL CONSIDERATION**

1076 **13.1 Statistical and Analytical Plans**

1077 This trial is single-armed and not powered to detect differences between groups. The study is
1078 designed to obtain a primary safety profile on patients in this age-group.

1079 This study is an early feasibility study that will test the safety of t:slim X2 with Control-IQ
1080 Technology in an outpatient setting. These studies would generate up to 75 days of closed-loop
1081 data. This sample size allows for subject withdrawal.

1082 **13.2 Statistical Hypotheses**

1083 **13.2.1 Primary Outcome**

1084 Number of subject with less than 6% time below 70mg/dL and less than 40% time above
1085 180mg/dL.

1086 **13.2.2 Secondary Outcome**

- 1087 1. % time spent <70 mg/dl, <60mg/dl, <54mg/dL, and <50mg/dL
- 1088 2. % time spent >180mg/dl, and >250mg/dl, >300 mg/dl
- 1089 3. % time spent between 70-180mg/dl
- 1090 4. % time spent between 70-150mg/dl
- 1091 5. Number of hypoglycemia below 70 mg/dL
- 1092 6. Number of carbohydrate treatments, as well as total amount of carbohydrates used for
1093 treatments.
- 1094 7. Time spent in closed loop
- 1095 8. Time with available CGM
- 1096 9. Number of subject with more than 70% time in 70-180mg/dL range with less than 4%
1097 time below 70mg/dL

1098 **13.2.3 Success Criteria / Goal**

1099 As a general rule, a session will be considered useful for data analysis if the subject completes
1100 close to 80% of the active study protocol. Sessions are considered separate: (i) Supervised
1101 Phase=complete at least 38 hours of AP; (ii) at home use=complete at least 56 hours of AP.

1102 *The primary goal will be considered met if the primary outcome is achieved for 65% or more of
1103 the subjects.*

1104 **13.2.4 Statistical Analysis Plan**

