1105 Proportions of subject matching primary criteria will be computed and directly compared to 65%
1106 (considered baseline). Further analysis will be performed using a chi² test of goodness of fit. Based
1107 on prior data in 6-12 year olds we anticipate a possible effect size of 0.64, which would allow to
1108 detect a difference with 70% power considering our sample size.

CLINICAL PROTOCOL

1109 Overall outcomes will be compared to the normative data below (values derived from the analysis
1110 of 30 6-12 year old T1D subjects using pumps and CGM and rounded for ease of use):

	Baseline	
	mean	std
% time below 50mg/dL	0.5%	0.5%
% time below 54mg/dL	1%	0.8%
% time below 60mg/dL	2%	1%
% time below 70 mg/dL	4%	2.5%
% time between 70-140mg/dL	40%	9%
% time between 70-180mg/dL	60%	9%
% time above 180mg/dL	35%	9%
% time above 250mg/dL	11%	5%
% time above 300mg/dL	4%	3%
Average CGM [mg/dL]	162.0	15.0

1111 This analysis will be performed using a single group one sided t-test for mean comparison for
1112 outcomes that can be assumed normally distributed and One-Sample Wilcoxon Signed Rank test
1113 for median comparison for the others, this analysis is not powered.

1114 Secondary outcomes will be reported for the entire period and for the supervised and home phases
1115 separately. Outcomes by phase will be compared to each other to assess possible loss of
1116 performances during the transition at home. For this purpose, McNemar's tests will be used to
1117 compare the supervised phase to the home phase for the primary outcome and secondary outcome
1118 # 6, 7, and 8. All other outcomes will be analyzed using repeated measure ANOVA. Significance
1119 of 0.05 will be used.

1120 This analysis is not powered.

1121 **Chapter 14: DATA COLLECTION AND MONITORING**

1122 **14.1 Case Report Forms and Device Data**

1123 The study data are collected through a combination of case report forms (electronic and paper) and
1124 electronic device data files obtained from the software and individual hardware components.
1125 These electronic device files and electronic CRFs are considered the primary source
1126 documentation.

1127 When data are directly collected in electronic case report forms, this will be considered the source
1128 data. Records will be maintained in accordance with ICH E6 and institutional regulatory
1129 requirements for the protection of confidentiality of participants.

1130 **14.2 Study Records Retention**

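### The hotel-to-home comparison in 13.2.4 is an unpowered test at 0.05 with no estimate or interval, so a non-significant result cannot show that control is kept at home

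*Combined protocol and SAP*

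**What the plan says.** Section 1.4 lists as a secondary aim to "Assess the safety profile of the system at home under parental/legal guardian(s" supervision. Section 2.1 sets the size: "Enrollment will proceed with the goal of completing 15 participants in this trial".

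The per-child primary criterion is in section 13.2.1: "Number of subject with less than 6% time below 70mg/dL and less than 40% time above" 180 mg/dL. Section 13.2.3 counts the primary goal as met at 65% of subjects or more and sets no separate threshold for the home phase.

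Section 13.2.4 treats the phases in two ways:

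- **Description.** "Secondary outcomes will be reported for the entire period and for the supervised and home phases" separately. The sentence names secondary outcomes only.
- **Testing.** "Outcomes by phase will be compared to each other to assess possible loss of" performance in the transition home. "For this purpose, McNemar's tests will be used to" "compare the supervised phase to the home phase for the primary outcome and secondary outcome" numbers 6, 7 and 8. For the rest: "All other outcomes will be analyzed using repeated measure ANOVA. Significance" is set at 0.05.

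The section then states that this analysis is not powered. It gives no interval for a phase result or a phase difference, no margin for an acceptable loss, no McNemar version, no sidedness for the phase tests and no rule for reading a non-significant result.

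**The concern.** Going home is the step at which round-the-clock staff supervision on site gives way to parental supervision with remote monitoring. It is where a loss of control would matter most for later use of the device. A test of no difference asks only whether hotel and home differ detectably in this sample. With 15 pairs, failure to detect a difference is weak evidence that there is none.

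Calling the analysis unpowered admits the low sensitivity, but the 0.05 verdict stays and nothing is planned that would show how large a loss the data leave open. A report written to this plan could state a p-value above 0.05 for the primary criterion and give neither the number of children who met it at home nor the range of losses compatible with the data.

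**Working it through.** **Inputs.** n = 15 (section 2.1). Alpha is 0.05 (section 13.2.4), taken as two-sided because the plan does not say. All 15 children are assumed usable in both phases. Let b be the number who meet the primary criterion in the hotel and fail it at home, and c the reverse.

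**1. The plan's own power figure.** Section 13.2.4 gives 70% power at effect size w = 0.64. For a chi-square goodness-of-fit test with 1 df, the noncentrality is 15 × 0.64² = 6.144 and the power is 69.8%. The figure reproduces, but it belongs to the test of the primary outcome against 65%. No power figure exists for the phase comparison.

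**2. McNemar p-values.**
- Exact: min{1, 2 × P(X ≤ min(b, c))}, with X ~ Bin(b + c, 0.5)
- Uncorrected: (b − c)²/(b + c) on 1 df
- Continuity-corrected: (|b − c| − 1)²/(b + c) on 1 df

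| Lost v gained | Net fall | Exact | Corrected | Uncorrected |
|---|---|---|---|---|
| 4 v 0 | 4 of 15 | 0.125 | 0.134 | 0.046 |
| 5 v 0 | 5 of 15 | 0.0625 | 0.074 | 0.025 |
| 6 v 1 | 5 of 15 | 0.125 | 0.131 | 0.059 |
| 6 v 0 | 6 of 15 | 0.031 | 0.041 | 0.014 |

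For example, the exact value at 5 v 0 is 2 × 0.5⁵ = 0.0625, and the uncorrected statistic at 6 v 1 is 25/7 = 3.57. At 5 v 0 the verdict depends on a version that the plan does not name. At 6 v 1, with the same net fall of a third of the children, none of the three versions is significant.

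**3. Power of the phase test**, by full multinomial enumeration at n = 15. The true changes are assumptions.
- True fall of one third, no child improving (b probability 1/3, c probability 0): exact 38%, uncorrected 79%.
- True fall of one third, 1 in 15 improving (0.40 and 0.067): exact 32%, uncorrected 49%.
- True fall from 95.5% to 70%, within-child correlation 0 to 0.2: exact 17%, uncorrected 45% to 52%. The 95.5% is the rate implied by the plan's effect size, 0.65 + 0.64 × √(0.65 × 0.35) = 0.955; the 70% is assumed.
- True fall from 95.5% to 65%, same correlations: exact 29%, uncorrected 57% to 67%.

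The continuity-corrected test has the same power as the exact test in these scenarios.

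**4. What intervals would show.**
- 5 v 0: loss 5/15 = 33 points, 95% Tango score interval about 6 to 58 points.
- 6 v 1: loss 33 points, interval about −1 to 61 points.
- Home phase alone, for example 9/15 = 60%: exact (Clopper-Pearson) 95% interval 32% to 84%.

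The score interval at 5 v 0 excludes zero although the exact p-value is 0.0625. The interval agrees with the uncorrected test and not with the exact one, which is a further reason to name the version.

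**5. Continuous outcomes.** For time in range, the half-width of a paired 95% interval is t(0.975, 14) × SD/√15. With an assumed SD of paired differences of 9 points this is 2.145 × 9/3.873 = 5.0 points, and 80% power needs a true loss of about 7.0 points. With SD 6 the two figures are 3.3 and 4.7; with SD 12 they are 6.6 and 9.3.

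**The case against.** A reader might infer that aim 1.4 rests on these tests alone. The documents do not support that. Section 13.2.4 reports the secondary outcomes by phase, so the home period has its own results for time below and above several glucose thresholds, for hypoglycemia counts and for secondary outcome 9, a per-child count with a tighter limit on time below 70 mg/dL than the primary criterion. Section 6.6 collects adverse events, device effects and device issues after home use, and section 11.5 has the Medical Monitor review severe hypoglycemia and ketoacidosis. The aim is worded as a profile, which is largely descriptive, and 13.2.4 does not name the phase tests as its answer.

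A reader might also infer that the plan treats non-significance as proof of no loss. It never says so, and it states that the comparison is not powered. Nor is non-significance the likely result under every version: uncorrected power reaches 79% in one scenario above, and 5 v 0 is significant uncorrected.

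Finally, a McNemar test on the primary criterion needs the paired two-by-two table, so the home count will exist in the analysis whether or not it is listed.

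All of this stands and narrows the point. It does not supply what is missing: a planned estimate of the hotel-to-home change, an interval around it, a stated commitment to report the primary criterion at home, and a rule for reading a p-value above 0.05.

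**Conclusion.** The point holds for the inferential phase comparison. As written, 13.2.4 can return a non-significant result when a third of the children (5 of 15, net) have lost the primary criterion at home. That happens under the exact and corrected tests at 5 v 0, and under the uncorrected test as well at 6 v 1. Such a result cannot show that control is kept at home, and the plan calls for nothing that would show how large a loss remains possible.

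This rests on a two-sided 0.05 level and on all 15 children being usable in both phases; the power figures and the paired SDs rest on assumed changes and spreads. The primary analysis against 65% is not affected. This is an inexpensive improvement worth making to a secondary comparison in a feasibility study.

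**What to change.** In section 13.2.4:

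1. Report the number of children who meet the primary criterion in the home phase, with an exact 95% confidence interval.
2. For each phase comparison, give the paired home-minus-hotel difference with a 95% interval as the main reading, in place of the 0.05 verdict. Use a paired-proportion interval for outcomes that are yes or no per child, and a mean or Hodges-Lehmann difference for the others. Secondary outcomes 6, 7 and 8, as listed in 13.2.2, are counts, amounts or durations and belong to the second kind unless a cut-off is defined.
3. If a p-value is kept for the primary criterion, name the McNemar version and choose one consistent with the interval.
4. State that a non-significant difference will not be reported as evidence of no loss at home.

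The cost is SAP wording and a few table columns, with no new data and no more participants. The downside is that intervals as wide as 32% to 84% will make the home result look less favourable than a bare p-value would.

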115	CHAPTER 12: MISCELLANEOUS CONSIDERATIONS.....	45
116	12.1 Prohibited Medications, Treatments, and Procedures	45
117	12.2 Participant Withdrawal.....	45
118	12.3 Confidentiality.....	45
119	CHAPTER 13: STATISTICAL CONSIDERATION	46
120	13.1 Statistical and Analytical Plans	46
121	13.2 Statistical Hypotheses	46
122	CHAPTER 14: DATA COLLECTION AND MONITORING	48
123	14.1 Case Report Forms and Device Data	48
124	14.2 Study Records Retention.....	48
125	14.3 Protocol Deviations	48
126	CHAPTER 15: ETHICS/PROTECTION OF HUMAN PARTICIPANTS	49
127	15.1 Ethical Standard	49
128	15.2 Institutional Review Boards	49
129	15.3 Informed Consent Process.....	49
130		

Protocol Summary

PARTICIPANT AREA	DESCRIPTION
Title	Safety of the Tandem t:slim X2 with Control-IQ Automated Insulin Delivery System in Preschoolers, age 2-6 Years Old.
Investigational Device	Tandem Control-IQ with G6 Continuous Glucose Monitor
Objectives	To assess study the safety profile of the Tandem t:slim X2 with Control-IQ system in children with T1D aged 2-6 years old under free living condition
Study Design	A single-arm, multi-center, clinical study
Number of Sites	3 independent clinical sites – sharing IDE and regulatory documentation only
Endpoint	Number of subjects with less than 6% time below 70 mg/dL and less than 40% time above 180 mg/dL.
Population	
Key Inclusion Criteria
 
 • Age ≥ 2 and < 6 years old at the time of visit 1 • Clinical diagnosis, based on investigator assessment, of type 1 diabetes for at least 3 months and using insulin at the time of enrollment • Use of an insulin pump in the past 3 months • Use of Dexcom G6 for at least 11 out of the last 14 days 
Key Exclusion Criteria
 
 • Hypoglycemia induced seizure or loss of consciousness in the past 3 months • Concurrent use of any non-insulin glucose-lowering agent • A condition, which in the opinion of the investigator or designee, would put the participant or study at risk.
Sample Size	Up to 15 participants
Participant Duration	About 14 days
Protocol Overview/Synopsis	48 hour hotel stay with 24/7 study team supervision followed by parental remote monitoring for 72 hours of at-home use

Study Visits and Procedures Schedule

	SCREENING	OPEN LOOP AT-HOME USE	PRE- ADMISSION CHECK-IN	HOTEL ADMISSION	CLOSED LOOP AT- HOME USE	POST- ADMISSION CHECK-IN
DURATION	ABOUT 3 HOURS		ABOUT 30 MINUTES	ABOUT 48 HOURS	ABOUT 72 HOURS	ABOUT 30 MINUTES

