1160 risks and possible benefits of participation will be provided. Consent forms will be IRB approved
1161 and the participant will be asked to read and review the document. The investigator or their
1162 delegate will explain the research study to the parent/guardian(s) and answer any questions that
1163 may arise. All participants will receive a verbal explanation in terms suited to their comprehension
1164 of the purposes, procedures, and potential risks of the study and of their rights as research
1165 participants. Parent/guardian(s) will have the opportunity to carefully review the written consent
1166 form and ask questions prior to signing.

1167 The parent/guardian(s) will sign the informed consent document prior to any procedures being
1168 done specifically for the study. The parent/guardian(s) may withdraw their child's consent at any
1169 time throughout the course of the trial. A copy of the informed consent document will be given to
1170 the parent/guardian(s) for their records. The rights and welfare of the participants will be protected
1171 by emphasizing to them that the quality of their medical care will not be adversely affected if they
1172 decline to participate in this study.

1173 A child participant is considered enrolled when the informed consent form has been signed.

1174 **15.3.2 Participant and Data Confidentiality**

1175 The study monitor, representatives of the IRB or device company supplying study product may
1176 inspect all documents and records required to be maintained by the investigator, including but not
1177 limited to, medical records (office, clinic, or hospital) for the participants in this study.

UNIVERSITY OF VIRGINIA

1178 The study participant's contact information will be securely stored at the clinical site for internal
1179 use during the study. At the end of the study, all records will continue to be kept in a secure
1180 location for as long a period as dictated by local IRB and Institutional regulations.

1181 Study participant research data, which is for purposes of statistical analysis and scientific reporting,
1182 will be transmitted to and stored at the University of Virginia Center for Diabetes Technology.
1183 This will not include the participant's contact or identifying information. Rather, individual
1184 participants and their research data will be identified by a unique study identification number. The

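### The sample size is stated three incompatible ways, the claimed allowance for withdrawal is not in the numbers, and it is not said whether a child who stops Control-IQ early is replaced or stays in the 65% denominator

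*Combined protocol and SAP*

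**What the plan says.** **Sample size.**
- Protocol Summary: "Up to 15 participants".
- Section 1.5.2: "Approximately 15 participants with Type 1 Diabetes Mellitus" will take part.
- Section 2.1: "Enrollment will proceed with the goal of completing 15 participants in this trial, approximately 5" per site, followed by "Up to 25 participants may sign the consent form".
- Section 15.3.1: "A child participant is considered enrolled when the informed consent form has been signed". Under that definition, up to 25 children can be enrolled.

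**Allowance for loss.** Section 13.1 says "These studies would generate up to 75 days of closed-loop" data, and then "This sample size allows for subject withdrawal". No withdrawal rate or number is given. Section 13.2.4 claims 70% power at an effect size of 0.64 for the stated sample size.

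**Children who stop.** Section 11.4.1 ends device use after one DKA episode, one severe hypoglycemia event, an investigator's safety concern or a participant's request. Section 7.2.2 ends participation for home ketones above 3.0 mmol/L. Section 12.2 keeps a withdrawn participant's data up to withdrawal. Section 13.2.3 treats a session as useful after at least 38 hours (supervised) or 56 hours (home), and sets the goal at 65% or more of the subjects without defining that group.

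**The concern.** A ceiling on participants and a target for completers are different rules for ending recruitment. They part company as soon as one child stops after starting Control-IQ, and the three sites run the trial independently (1.5.3), so they could apply different rules.

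The primary goal is a percentage of children in a safety trial, and several of the protocol's reasons for stopping are themselves poor outcomes. If the analysed group becomes the children who finished, either because 2.1 recruits to completion or because 13.2.3 discards short sessions, children who did badly can leave the denominator. The percentage then rises with no change in the device. With 15 children, one or two such losses decide whether the goal is met. The 13.1 sentence also tells the reader that losses have been provided for, when neither of the plan's figures provides for any.

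**Working it through.** **1. Reproduce the 75 days.** Closed-loop time per child is 48 h in the hotel plus 72 h at home, which is 5 days. 15 × 5 = 75. The stated figure is reproduced only if all 15 children finish both phases.

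**2. Reproduce the 70% power.** Inputs from 13.2.4 are effect size w = 0.64 and a chi-square goodness-of-fit test, with 1 df because the outcome is binary. Alpha 0.05 is stated there for the comparison of phases and is assumed here for the primary test. Noncentrality = N × w². At N = 15 it is 15 × 0.4096 = 6.144, and power is 69.8%, which matches. N = 14 gives 66.8%, N = 13 gives 63.6% and N = 12 gives 60.1%. The power figure also uses all 15.

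**3. What an allowance would need.** No dropout rate is given, so a range is assumed.

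| Assumed dropout d | Starters for 15 completers, 15/(1−d) rounded up | Expected completers from 15 starters | Full-completer days |
|---|---|---|---|
| 5% | 16 | 14.25 | 71.25 |
| 10% | 17 | 13.5 | 67.5 |
| 15% | 18 | 12.75 | 63.75 |
| 20% | 19 | 12 | 60 |

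Every entry in the second column exceeds the synopsis ceiling. The only slack is over-enrolment under 2.1, which that ceiling rules out and 13.1 does not mention. Conversely, if 15 must complete and 12.2 keeps partial data from stoppers, the total could exceed 75 days.

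**4. Sensitivity of the goal in simple counts.** 65% of 15 is 9.75, so 10 of 15 (66.7%) are needed.
- Dropping alone: with 15 starters, 9 successes and 2 stopped failures, 9/15 = 60.0% misses the goal, but 9/13 = 69.2% meets it.
- Dropping and replacing: with 15 completers, 10 successes and 1 replaced stopper, 10/15 = 66.7% meets the goal, but 10/16 = 62.5% misses it.

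**5. Chance of meeting the goal.** Assumptions: the true success rate per starter is p = 0.60, a share s of starters stop, and every stopper is a failure. The success rate among children who do not stop is p/(1−s): 0.632 at s = 5%, 0.667 at 10% and 0.75 at 20%.
- All starters counted: P(Bin(15, 0.60) ≥ 10).
- Dropped, not replaced: M ~ Bin(15, 1−s) remain, successes ~ Bin(M, p/(1−s)), and the goal is met at 0.65M or more.
- Dropped and replaced: P(Bin(15, p/(1−s)) ≥ 10).
- Replaced but counted as failures: K stops occur before the 15th completer, and the goal is met at 0.65(15 + K) or more successes.

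| Stop rate s | All 15 starters counted | Dropped, not replaced | Dropped and replaced | Replaced, counted as failures |
|---|---|---|---|---|
| 0% | 40% | 40% | 40% | 40% |
| 5% | 40% | 45% | 50% | 36% |
| 10% | 40% | 55% | 62% | 34% |
| 20% | 40% | 78% | 85% | 35% |

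At 10% and 20%, dropping stoppers accounts for most of the rise and replacement adds about 7 points. Replacement with stoppers kept as failures produces no inflation.

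**The case against.** The strongest reply is that the harm is hypothetical. Section 2.1 states a goal, and nowhere do the documents tell a site to recruit another child for each one who stops. The 25 consents have an ordinary purpose, since screening follows consent and admissions can be cancelled (5.3, 5.4). Section 12.2 keeps withdrawn children's data, which weighs against their vanishing from the analysis. No stop rate is given, and 10% or 20% within five days may be high. The primary outcome is CGM time below 70 and above 180 mg/dL, so a child stopped for DKA, ketones or severe hypoglycemia has not by definition failed it, and a stop on request may have nothing to do with glucose. Severe hypoglycemia and DKA are reportable and reviewed by the Medical Monitor whatever happens to the percentage, and more than one of either may pause the study (11.4.2). Finally, 75 days is worded as a maximum, and an early feasibility study can describe one target loosely.

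Most of this stands as a limit on the claim. Replacement is a possibility left open by 2.1, and the size of any bias is unknown. What does not fall away is the gap itself. Section 12.2 says whose data are used, but not whether that child is replaced or counted among the subjects in 13.2.3. An upper limit of 75 days is legitimate, but it cannot support the sentence that follows it.

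**Conclusion.** The point holds as a conflict between sections and a missing rule. The synopsis, 1.5.2 and 2.1 cannot all govern recruitment once a child stops early. The allowance in 13.1 is unsupported, because 75 days and 70% power both need all 15 children. The primary denominator is undefined for a child who stops after starting Control-IQ.

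Two stronger readings are tempting and not supported. A reader might infer that the protocol replaces every child whom the device harms; the text neither provides for nor forbids this. A reader might also infer that replacement is the source of the bias, so that no inflation arises without it. The calculation shows otherwise: dropping stoppers alone raises the chance of meeting the goal from 40% to 55% or 78%, and replacement takes it to 62% or 85%.

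Those figures rest on an assumed true rate of 60%, assumed stop rates of 10% and 20%, and all stoppers being failures. With no stops the effect is zero, and with stoppers who would have succeeded it could go the other way. The power check assumes alpha 0.05. The correction is worth making before any results are seen.

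**What to change.** 1. **Synopsis, 1.5.2 and 2.1:** state one maximum number of children who start Control-IQ. Say that children lost before first activation (screen failure, cancelled admission) may be replaced within the 25 consents, and that children who stop after activation are not. Keep the consent-based definition of enrolment in 15.3.1, but use a separate term for starters.
2. **13.2.3:** define the primary denominator as all children who start Control-IQ. A child who stops early stays in it and is scored as not meeting the primary outcome. Add a sensitivity analysis that scores such children on their CGM data up to the stop, in line with 12.2. Say that the 38-hour and 56-hour limits do not remove a child from this denominator.
3. **13.1 and 13.2.4:** replace the allowance sentence with a statement that up to 75 days will be obtained if no child stops early, and note that the 70% power assumes all 15 are analysed.

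The cost is wording in a few sections. Fewer than 15 children may complete, so there may be somewhat less closed-loop data, and the observed success percentage may be slightly lower. No clinical rule changes.
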